7.6.1 Permitted Concomitant Therapy Requiring Caution and/or Action

Details for specific medications that require action and/or caution while on study in subjects potentially taking infigratinib are provided in Appendix 1 (Section 17.1). The rationale for these medications is provided below.

Infigratinib is characterized by pH-dependent solubility, and therefore, medicinal products that alter the pH of the upper GI tract may alter the solubility of infigratinib, and limit bioavailability. These agents include, but are not limited to, proton pump inhibitors (eg, omeprazole), H₂-antagonists (eg, ranitidine) and antacids. Proton pump inhibitors are prohibited due to their long PD effect and should be replaced with H₂-antagonists or antacids. Study drug should be taken ≥ 2 hours before or 10 hours after dosing with H₂-antagonists. Antacids, locally-acting acid neutralizing agents, are to be separated from study drug doses by 2 hours.

Infigratinib a substrate of CYP3A4. If anticoagulation is required, heparin and/or low-molecular-weight heparins or direct thrombin inhibitors and/or Factor Xa inhibitors that are not metabolized by CYP3A4 (eg, dabigatran, edoxaban) to be used. Anticoagulants that are CYP3A4 substrates and have a narrow therapeutic index (eg, warfarin sodium or any other coumadin-derivative anticoagulants or certain direct thrombin inhibitors [eg, argatroban] or Factor Xa inhibitors [eg, rivaroxaban]) should be used with caution and frequency of monitoring increased. Refer to Section 7.6.2 for further information on CYP3A4.

Infigratinib was shown in vitro to inhibit the drug transporter breast cancer resistance protein (BCRP), with an IC₅₀ of 210 nM. While the clinical relevance of this inhibition is unknown, drugs transported by BCRP should be used with caution.

Anti-emetics are recommended as clinically appropriate at the first sign of nausea and vomiting or as prophylaxis to prevent emesis, along with supportive care according to clinical practice guidelines, with the following considerations:

- Ondansetron has a known risk for Torsade de Pointes (TdP), and therefore should be used with caution. Palonosetron may be used as an alternative.
- Aprepitant (brand name: Emend[®]) is both a sensitive substrate and a moderate CYP3A4 inhibitor and is prohibited with infigratinib. Similarly, the use of other agents in the neurokinin-1 (NK-1) receptor antagonist class (casopitant and fosaprepitant) is limited by drug interactions and is prohibited with infigratinib.

Preliminary data have shown that infigratinib has no effect on cardiac conduction or ECG intervals (see current version of the infigratinib Investigator's Brochure). Medications that have the possible, conditional, or established risk of QTc prolongation or causing TdP are allowed but

should be used with caution while on study. Investigators at their discretion may co-administer such medications, but subjects should be carefully monitored.

See Appendix 1 (Section 17.1) for list of drugs that need to be used with caution. Please note that the list might not be comprehensive.

Subjects with newly detected NMIBC or low-grade/noninvasive UTUC can be treated with non-systemic standard therapy, such as BCG instillation, intravesical treatment, and mitomycin gel.

7.6.2 *Prohibited Concomitant Therapy*

A concomitant medication is considered prohibited if it appears on any of the prohibited medication lists for any clinical pharmacology property of the drug (eg, CYP, BCRP).

Details for specific medications prohibited while on study are provided in Appendix 2 (Section 17.2). The rationale for the restricted medications is provided below.

Other investigational therapies must not be used while the subject is on the study. Other than study drug, anticancer therapy (eg, chemotherapy, biologic or radiation therapy, surgery) must not be given to subjects while the subject is on the study drug. If such agents are required, then the subject must be discontinued from study drug but will continue in the study with all described study-related assessments, including assessment for recurrence (conducted until metastatic recurrence [see Section 9.8]) as well as use of other anticancer therapy and survival. Exceptions are nonsystemic treatments for low-grade/noninvasive UTUC or NMIBC, such as intravesical treatment, mitomycin gel, or BCG instillation.

Proton pump inhibitors are prohibited; see Section 7.6.1 for rationale.

Strong and moderate inhibitors of CYP3A4 such as the ones listed in Appendix 2 (Section 17.2) are prohibited because infigratinib is a likely substrate of this isoenzyme; these include the anti-emetic aprepitant (brand name: Emend) and other agents in the NK-1 receptor antagonist class (casopitant and fosaprepitant), as described in Section 7.6.1.

Strong and moderate inducers of CYP3A4 are prohibited because their usage may decrease the exposure of infigratinib. Therefore, agents such as those listed in Appendix 2 (Section 17.2) are prohibited. Please note that the list may not be exhaustive.

Subjects must also avoid the consumption of grapefruits, grapefruit juice, grapefruit hybrids, pomegranates, star fruits, pomelos, Seville oranges or juice within 7 days before the first dose of study drug and throughout the treatment period due to a potential CYP3A4 interaction with study drug.

Medications that increase the serum levels of phosphorus and/or calcium are prohibited. Chinese herbal medicines and Chinese patent medicines for the treatment of cancer are not allowed during the treatment period.

7.6.3 ***COVID-19 Vaccinations***

The effect of coronavirus disease 2019 (COVID-19) vaccines has not been studied in combination with infigratinib; hence the safety and efficacy of either agent when used in combination are unknown (ie, vaccination before, during, or after infigratinib treatment has not been studied, and the efficacy and safety of COVID-19 vaccines in the presence of infigratinib, as well as the efficacy and safety of infigratinib in the presence of a COVID-19 vaccine, are unknown).

There is no detailed or conclusive information on studies conducted with the COVID-19 vaccines in subjects receiving any anticancer therapies, or in patients with cancer. In general, COVID-19 vaccines may be administered before, during, and after study participation, if determined to be safe in the clinical judgement of the treating physician/study investigator. The treating physician/study investigator should assess the risk for each individual study subject for receiving the vaccine in the context of the study.

Whenever feasible, vaccinations should be administered at least 30 days prior to randomization

All applicable guidelines should be followed, and vaccinations should adhere to the manufacturer's guidelines for eligibility and contraindications to receive the vaccine ([Garassino 2020](#); [ASCO 2021](#); [Pergam 2021](#)). Subjects vaccinated for COVID-19 should be closely monitored, and any observed AEs/SAEs should be reported as outlined in Section [10.5.1](#).

7.7 **Non-drug Therapies**

Any significant non-drug therapies (including physical therapy, herbal/natural medications, and blood transfusions) administered from the time of first dose of study drug through 30 days after last dose are to be recorded for each subject on the Concomitant Therapy page of the eCRF. Dates for the start and stop of each therapy are to be recorded, as well as the reason for administration (particularly if administered for an AE).

Non-drug therapies are prohibited if they appear on any of the prohibited medication lists for any clinical pharmacology or PK property of the drug (eg, CYP, BCRP) (in Appendix 2 [Section [17.2](#)]).

8 SUBJECT DISCONTINUATION AND STUDY TERMINATION

8.1 **Subject Discontinuation**

8.1.1 ***Discontinuation of Study Drug***

Discontinuation of study treatment does not represent withdrawal from the trial.

If study treatment is permanently discontinued for reasons other than subject's withdrawal of consent, the subject will remain in the study to be evaluated for all study prespecified assessments (such as safety follow-up, efficacy, etc.) See Section [2](#) for data to be collected at the time of discontinuation of study treatment and follow-up.

Subjects must be discontinued from study drug for:

- Local/regional or contralateral invasive or metastatic recurrence (whichever occurs first) by BICR:
 - Subjects should remain on study treatment until local/regional or contralateral invasive or metastatic recurrence is confirmed by BICR.
 - All subjects' imaging (CT/magnetic resonance imaging [MRI] scans) will be read locally and submitted for BICR read, together with any supporting report (including pathology and cytology reports) if a biopsy was conducted (for example, if recurrence was suspected). A central read should be requested at the time of investigator-assessed disease recurrence for confirmation by BICR.
 - If BICR confirms recurrence (local/regional or contralateral invasive or metastatic recurrence, whichever occurs first), the subject must be permanently discontinued from study treatment.
 - If locally diagnosed local/regional or contralateral invasive or metastatic recurrence is not confirmed by BICR, treatment continuation is allowed at Investigator's decision.
 - BICR diagnosis of a local/regional or contralateral invasive or metastatic recurrence, independently from and undiagnosed by local team, will not be communicated to the clinical site.
- Pregnancy.
- 52-week treatment phase completed.
- AE that leads to substantial changes in individual risk-benefit considerations.
- Delay of study drug administration of >14 days (exclusive of scheduled dose interruption, with exceptions noted in Section 7.2.5.1).
- Death.

In addition, subjects may be discontinued from study drug for any of the following reasons:

- New medical condition that does not allow continuation of study drug compliance.
- Protocol deviation, including non-compliance with dosing regimen and retroactive failure to fulfill study entry criteria.
- Lost to follow-up (defined as no contact after 3 documented attempts by telephone followed by 1 attempt via letter [eg, certified mail, if available]).
- Subject request; if a subject withdraws consent from study treatment, it is required to document if the subject agrees or not 1) with continuation with study assessments; 2) to be followed for long-term follow-up and initiation of new anticancer therapies.
- Investigator request
- Use of other investigational therapies.

- Use of anticancer therapy (eg, chemotherapy, biologic or radiation therapy, surgery) other than the study drug. Exceptions are non-systemic treatments for low-grade or noninvasive UTUC or NMIBC, such as intravesical treatment, mitomycin gel, or BCG instillation.

The investigator must notify the sponsor/representatives if a subject is discontinued prematurely from study drug for any reasons, including reasons other than radiological or pathologic local/regional or contralateral invasive or metastatic recurrence. Subject's withdrawal from treatment must be documented and must also capture subject's permission or not to be followed for long-term follow up and anticancer therapy initiation. At the time of discontinuation of study drug, subjects are to complete the EOT visit (no later than 5 days after treatment discontinuation), the 30-day Follow-up visit (according to [Table 2](#) and Section [9.7](#)), and subsequent follow-up visits and assessments, according to [Table 2](#), Section [9.8](#), and Section [9.9](#).

The reason for treatment discontinuation is to be documented in the eCRF including identifying one reason as the primary reason for treatment discontinuation. The investigator should make every effort to determine why a subject is lost to follow-up or withdraws consent and record this information in the eCRF. Further, if a subject is discontinued from treatment due to protocol deviation or Investigator's request, specifics are to be recorded in the eCRF.

8.1.2 Discontinuation from Study

Subjects have the right to withdraw from the study at any time without prejudice. Pending the criteria for which the subject withdraws consent, as listed below, those specified assessments must be discontinued and no further assessments conducted. Further attempts to contact the subject are not allowed unless safety findings require communication or follow-up.

Subjects may be discontinued from the study for the following reasons:

- Subject's formal withdrawal of informed consent. If a subject withdraws consent from study participation, the level of withdrawal must be documented. Below are the possible levels of subject's withdrawals:
 - Full withdrawal: withdrawal from all study treatments, procedures, assessments, and any type of follow-up (survival, new anticancer therapy, etc.)
 - Withdrawal from all study assessments or procedures; survival follow-up is permitted, together with collection of data related to initiation of new anticancer therapy.
 - Withdrawal from survival follow-up (subject or family cannot be contacted; public record data can be reviewed).
 - If a subject withdraws from the study, the subject may request destruction of any samples taken and not tested, and the investigator must document this in the study records and notify the sponsor immediately.
- Investigator request.
- Lost to follow-up (defined as no contact after 3 documented attempts by telephone followed by 1 attempt via certified letter).
- Discontinuation of the study by the sponsor.

- Protocol deviation.
- Study complete.
- Death.
- Other.

The reason for discontinuation from the study is to be documented in the eCRF, including the exact level of subject's withdrawal from the study. The investigator should make every effort to determine why a subject is lost to follow-up or withdraws consent and record this information in the eCRF. Further, if a subject is withdrawn due to protocol violation or Investigator's request, specifics are to be recorded in the eCRF.

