5.3 Time on Study and End of Study Definition

End of study is defined as 1 year after the final number of confirmed DFS events by BICR is reached (planned number of confirmed DFS events is 70). The expected duration of the study is approximately 5 years.

After the EOS (1 year after the DFS primary analysis), subjects will continue to be followed for OS (under a separate protocol) for approximately 14 years, or all of the subjects die or drop from this follow up, whichever is earlier, referred to as long-term OS follow-up (Section 9.9).

The duration of time spent on study treatment will vary for individual subjects. Subjects will receive study treatment for a maximum of 52 weeks (13 cycles), or until BICR-confirmed local/regional or contralateral invasive or metastatic recurrence (whichever occurs first), or until other criteria specified in Section 8.1.1 are met, whichever occurs first. Subjects who complete 52 weeks of treatment and subjects who discontinue study treatment for any reason (except withdrawal of consent) will remain in the study and will be followed up until metastatic recurrence, including after initiation of a non-study anticancer therapy, as described in Section 9.8. Use of anticancer therapy will be collected for all subjects, including from the time of study treatment discontinuation, regardless of reason for discontinuation. All subjects will be followed up for survival status and use of anticancer therapy for 1 year after the final number of DFS events are reached (ie, EOS) (see Section 9.9). After the final DFS goal is reached, subjects will continue to be followed for long-term OS follow up for approximately 14 years as described above and in Section 9.9.

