9.9 Survival Follow-up and New Antineoplastic Therapies

After either BICR-confirmed metastatic recurrence, or investigator-confirmed metastatic recurrence if BICR-confirmed local/regional or contralateral recurrence has already occurred, subjects will be followed up for survival status every 6 months for 1 year, then annually thereafter (via telephone or office visit) for 1 year (± 14 days) after the final DFS event goal is reached (ie, EOS).

Antineoplastic therapies since discontinuation of study treatment should also be collected for 1 year (± 14 days) after the final DFS event goal is reached (ie, EOS). Use of anticancer therapy will be collected for all subjects, including from the time of study treatment discontinuation, regardless of reason for discontinuation. For subjects started on a non-study related anticancer therapy after discontinuing from study treatment, imaging assessment of disease status should continue until metastatic recurrence by BICR or metastatic recurrence by investigator assessment if local/regional or contralateral invasive recurrence by BICR has already occurred.

If a subject requests withdrawal of consent specifically from survival follow-up, this request must be documented in the subject's medical record. In such cases, the site staff may use public information source (such as county records) to obtain information about survival status and only as appropriate per local regulations.

After the EOS (1 year after the DFS primary analysis), subjects will continue to be followed for OS (under a separate protocol) for approximately 14 years, or all of the subjects die or drop from this follow up, whichever is earlier, referred to as long-term OS follow up. The data for the long-term OS will be reported in a separate study report.

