6 DEFINITIONS

Baseline

In general, the baseline value will be considered the last measurement observed prior to taking the first dose of study treatment. For ECG, if a set of triplet ECG are the last ECG collected prior to taking the first dose of study treatment, the average of the triplet ECG will be considered as baseline.

For subjects who are randomized and never receive study treatment, the baseline value will be the last assessment before randomization (on the day of or before randomization).

Investigational Product/Study Treatment

‘Investigational product’ or ‘study treatment’ is used to reference only infigratinib or placebo.

Long-term Follow-up Phase

The long-term follow-up phase begins after the safety follow-up visit and continues until death or full consent withdrawal. Efficacy assessments including radiographic assessments, cystoscopy and urine cytology will continue to be performed until recurrence by BICR (local/regional invasive or metastatic) or metastatic recurrence by investigator assessment, whichever comes later. Subjects who develop recurrence by BICR (local/regional invasive or metastatic) or metastatic recurrence by investigator assessment prior to the long-term follow-up phase will not be followed for disease status during the long-term follow-up phase. After that time, subjects will be followed for survival every 6 months for 1 year, then annually thereafter (via telephone or office visit) for 1 year after the time when the final DFS event goal is reached (ie, EOS).

Overall Survival Time (OS)

Overall survival time is calculated as the number of months from randomization to death (date of death - date of randomization + 1)/(365.25/12). Subjects who have not died (no record of death) or are lost to follow up will be censored at the date of last known to be alive. Subjects who

withdraw consent for study participation, including consent to be followed, will be censored on the date of withdrawal.

Metastasis-free Survival Time (MFS)

The investigator reviewed MFS is defined as the time from randomization to any metastatic recurrence as determined by the investigator or death due to any cause, whichever occurs earlier. Subjects without documented metastatic recurrence and are still alive, will be censored at the last radiology assessment, or at the time of randomization if no radiology disease assessments are performed after the baseline visit.

Disease-free Survival Time (DFS)

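### Protocol 8.1.2 lets a consenting randomized subject be taken out of the study for a protocol deviation, at the investigator's request or for another reason, which conflicts with the retention rules in Protocol 5.3 and 8.1.1 and SAP Section 6

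*Protocol*

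**What the plan says.** Three places set a retention rule.

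- Protocol 5.3: "subjects who discontinue study treatment for any reason (except withdrawal of consent) will remain in the study and will be followed up until metastatic recurrence". The same sentence covers subjects who complete the 52 weeks, and the section also promises survival follow-up of all subjects until one year after the last required DFS event.
- Protocol 8.1.1: "If study treatment is permanently discontinued for reasons other than subject's withdrawal of consent, the subject will remain in the study". Safety and efficacy assessments then carry on as scheduled.
- SAP Section 6: the long-term follow-up phase "continues until death or full consent withdrawal".

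Protocol 8.1.2 then opens a list with "Subjects may be discontinued from the study for the following reasons". It contains formal withdrawal of consent (with graded levels), investigator request, loss to follow-up, sponsor termination, protocol deviation, study complete, death and other. Its closing paragraph adds: "if a subject is withdrawn due to protocol violation or Investigator's request, specifics are to be recorded in the eCRF". It does not require imaging or survival contact to continue after such a removal.

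Investigator request and protocol deviation already appear in 8.1.1 as reasons to stop study drug. The second is spelled out there: "Protocol deviation, including non-compliance with dosing regimen and retroactive failure to fulfill study entry criteria".

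On survival status, Protocol 9.9 provides for a public-record search when a subject withdraws consent specifically from survival follow-up: "In such cases, the site staff may use public information source". It describes no such search for subjects lost to follow-up.

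**The concern.** The same event has two consequences. Under 8.1.1 a deviation or an investigator's decision stops the drug and the subject stays under observation. Under 8.1.2 it may end participation altogether, although the subject has not withdrawn consent.

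At stake is the completeness of outcome data in the ITT population (Protocol 11.1, SAP 7.1). A removed subject remains in that population, but later events are not seen. DFS and MFS would be censored at the last qualifying assessment, and OS at the date last known alive. If removals were related to prognosis and differed by arm, the censoring would be informative. This loss is avoidable, because the subject has not refused follow-up.

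**Working it through.** **Step 1. The texts side by side.**

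| Event in a consenting subject | Protocol 8.1.1 | Protocol 8.1.2 |
|---|---|---|
| Protocol deviation | May stop drug; stays in the study | May leave the study; record specifics |
| Investigator request | May stop drug; stays in the study | May leave the study; record specifics |
| Other | Not listed | May leave the study |

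Protocol 5.3 and SAP Section 6 agree with the 8.1.1 column. The first two rows have incompatible outcomes, and no sentence says which section governs.

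**Step 2. What happens to the data.** Under Protocol 11.3.3 and SAP Section 6, a subject with no event is censored as follows:

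- DFS: at the last radiology assessment or, where the cystoscopy condition for subjects with a bladder is not met, at the last complete recurrence assessment.
- MFS: at the last radiology assessment.
- OS: at the date last known alive.

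Neither document has a separate rule for subjects removed by the investigator. SAP 8.9 drops sensitivity analyses.

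**Step 3. The design figures reproduce.** Inputs from Protocol 11.2: HR 0.5, one-sided alpha 0.025, about 80% power, 70 events, 218 subjects, placebo recurrence of 46% by 2 years then 5% a year, 3-year uniform accrual, 1-year follow-up and 10% yearly dropout.

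- Freedman: events = [(1 + HR)/(1 − HR)]² × (1.960 + 0.842)² = 9 × 7.85 ≈ 70.6, so 71 against the stated 70. Power at 70 events is 79.6%.
- Schoenfeld: 4 × 7.85/(ln 0.5)² ≈ 65.3, so 66 events. Power at 70 events is 82.6%.
- Expected events at year 4, integrating a piecewise-exponential placebo hazard: 44.4 placebo + 25.4 infigratinib = 69.8.

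The sample size contains no arithmetic error.

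**Step 4. Removal unrelated to outcome.** The rates are assumed, because the documents give none. They apply to both arms, on top of the planned dropout.

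| Extra removal per year | Expected events at year 4 | Schoenfeld power at that count |
|---|---|---|
| None | 69.8 | about 82.6% (70 events) |
| 2% | 68.5 | 81.8% |
| 5% | 66.7 | 80.8% |
| 10% | 63.6 | 78.9% |

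The analysis waits for about 70 events, so removal of this kind mainly delays it. The issue is possible bias more than power, and the documents give nothing from which to size a bias.

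**The case against.** **The list is a set of end-of-study codes.** Protocol 9.10 sends investigators to 8.1.2 for the primary end-of-study reason. That explains entries such as study complete and death, and it is a good reason not to delete other outright. It does not explain the closing sentence of 8.1.2, which speaks of a subject being withdrawn for a protocol violation or at the investigator's request.

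**Sections 5.3 and 8.1.1 govern stopping drug and are not a complete exit rule.** This stands in part. Read as exhaustive, they would also rule out loss to follow-up and sponsor termination, which are legitimate exits. The conflict is confined to the three entries above.

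**Other text limits the risk.** Non-compliance and retroactive eligibility failure are spelled out only in 8.1.1. Post-baseline imaging goes to BICR (Protocol 10.1), imaging continues after new anticancer therapy (Protocol 5.1 and 9.8), and unblinding must not lead to withdrawal (Protocol 7.3). All of this lowers the chance of misuse, but none of it closes the route in 8.1.2.

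**Stronger readings to resist.** A reader might infer that outcomes are being lost in a treatment-related way. The documents do not show that, and the trial is double-blind. A reader might also assume that 3% to 5% of 218 subjects are removed (6.5 to 10.9), that three infigratinib events are lost and no placebo events, and that an HR of 0.50 becomes 0.50 × 22/25 = 0.44. The rate is invented. Moreover, the infigratinib arm's expected event fraction is 25.4/109 = 23%, so placing every removal in that arm loses only 6.5 × 0.23 ≈ 1.5 to 10.9 × 0.23 ≈ 2.5 events. Reaching three needs the further assumption that removed subjects recur more often.

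**The public-record point rests on silence.** This is fair: Protocol 9.9 does not forbid a search for subjects lost to follow-up. It is a secondary matter.

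**Conclusion.** The contradiction is in the text and should be reconciled. A site could comply with 8.1.2 and still end recurrence and survival follow-up that 5.3, 8.1.1 and SAP Section 6 require for a consenting randomized subject. The resulting censoring could be informative if removals differed by arm. With no removal rate and no evidence of an arm difference in the documents, its size cannot be stated and no HR shift should be claimed.

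The present consequence is limited. The study was terminated early, and the SAP tests no hypotheses (Section 5) and describes time-to-event endpoints by Kaplan-Meier only (Section 8.1). What remains exposed is the Kaplan-Meier description, where few events make each lost outcome count for more. SAP 8.3 already summarizes reasons for leaving the study, which would show how often this happened but would not recover the outcomes.

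**What to change.** - **Protocol 8.1.2:** remove investigator request and protocol deviation, together with the matching closing sentence on withdrawal. Keep both in 8.1.1 as they stand, as reasons to stop study drug.
- **Other:** keep it only as an end-of-study code with the reason specified, and state that it does not by itself end follow-up of a consenting subject.
- **Exit rule:** state that follow-up ends only through a documented level of consent withdrawal, loss to follow-up, death, or study completion or termination.
- **Protocol 9.9 (secondary):** extend the public-record survival check to subjects lost to follow-up, where local rules allow.
- **Terminated study:** in the SAP 8.3 summary of study discontinuation, show by arm how many subjects left for these three reasons.

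The cost is a small change to protocol wording and eCRF options, some record searches and one breakdown in a planned table. No visits are added beyond those already scheduled.
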